### 13.3 Analysis of Secondary Endpoints

#### *Phase I Study:*

CONFIDENTIAL

This document is confidential. Do not disclose or use except as authorized.

Secondary endpoints in the phase I trial include PK assessments. Pharmacokinetic parameters including half-life,  $C_{max}$ , AUC, volume of distribution, and clearance will be determined using non-compartmental methods. Standard descriptive statistics (mean, standard deviation, median, range) will be presented on all parameters. These analyses will be performed in all patients accrued to the phase I component of the trial.

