# 8. PHARMACEUTICAL INFORMATION

## 8.1 Duvelisib

### 8.1.1 Description

Duvelisib is a potent oral inhibitor of the delta- and gamma-isoforms of PI3K. Duvelisib is rapidly absorbed following oral administration, with maximal concentrations occurring approximately 0.5 to 2 hours after dosing. Exposure (AUC) increased proportionally with doses through 75 mg PO BID. The half-life was 7 hours, regardless of dose. The mean pre-dose steady state plasma concentration following 25 mg BID was 425 ng/mL, indicating suppression of PI3K-delta (IC90=361 ng/mL) and PI3K-gamma (IC50=429 ng/mL) throughout the dosing interval. Pharmacodynamic studies confirmed rapid, profound and sustained inhibition of AKT phosphorylation by duvelisib in CLL cells, as well as decreased levels of chemokines such as CCL3 and CCL4, which are important for

CONFIDENTIAL

This document is confidential. Do not disclose or use except as authorized.

lymphocyte trafficking. The MTD of duvelisib as monotherapy for CLL has been determined to be 75 mg BID, but the recommended phase 2 dose is 25 mg bid, which was chosen as the optimal balance of safety and efficacy.

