The venetoclax formulation currently used in clinical studies is a tablet formulation with strengths of 10, 50, and 100 mg. The tablet formulation was orally administered after a low-fat meal. Food increased the bioavailability of venetoclax by 3- to 4-fold. Preliminary pharmacokinetic results indicated that the absorption of venetoclax after the oral dosing was relatively slow. Venetoclax plasma concentrations peaked at approximately 5 to 8 hours after dosing. Mean harmonic terminal phase half-life from 17 to 41 hours and the mean oral clearance was approximately 13 L/hr after a single dose. Preliminary data did not suggest apparent pharmacokinetics differences among subjects with CLL/SLL, NHL, Multiple Myeloma (MM), Acute Myeloid Leukemia (AML), or SLE. The combined data from subjects with CLL/SLL and NHL suggested that venetoclax exposure was approximately dose proportional across the 150 to 800 mg dose levels at steady state. Additional information about venetoclax is available in the package insert.

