### 9.5 Pharmacokinetic (PK) Testing (Phase I) :

In the phase I study, PK testing for duvelisib will be performed at baseline, 0.5, 1, 2, 4, 6, 8, 10, , and 24 hours following the initial dose of duvelisib on Day 1. PK testing will be performed at baseline, 0.5, 1, 2, 4, 6, 8, 10, and 24 hours following the initial venetoclax dosing on Day 8 to analyze both duvelisib and venetoclax PK. The 10-hour post dose PK is strongly encouraged, but optional. PK analysis for both drugs will be performed at pre-dose, 1 and 4 hours in subsequent weeks to assess steady-state levels prior to cycle 2 at each venetoclax dose escalation.

	Cycle 1 Day 1 (duvelisib)	Cycle 1 Day 8 (duvelisib + venetoclax)	Cycle 1 On days of venetoclax dose escalation
Pre-dose (-2 hrs)	X	X	X
0.5h post dose (± 5 mins)	X	X	
1h post dose (± 5 mins)	X	X	X
2h post dose (± 5 mins)	X	X	
4h post dose (± 15 mins)	X	X	X
6h post dose (± 15 mins)	X	X	
8h post dose (± 15 mins)	X	X	
10h post dose (± 15 mins) (optional)	X	X	
24h post dose (± 15 mins)	X	X	

CONFIDENTIAL

This document is confidential. Do not disclose or use except as authorized.

Blood will be collected in vacutainers (4.0 ml BD Vacutainer® K2 EDTA Purple Top) at above mentioned time points and centrifuged (within 30 minutes) at a standard speed and time in a refrigerated centrifuge to process the plasma. The processed plasma will be divided and transferred into two cryotubes (primary and secondary; 2X1.8 mL white cryotubes) using transfer pipette. The cryotubes will be stored at -80°C freezer until shipment to bioanalytical laboratory.

Duvelisib and Venetoclax PK analyses will be performed at:

inVentiv Health  
[name],  
Quebec, Quebec, G1P 0A2  
CANADA

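### Venetoclax half-life, apparent clearance and apparent volume cannot be reliably estimated non-compartmentally from 24 h sampling, and the Day 1 duvelisib 24 h sample needs an exclusion rule

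*Combined protocol and SAP*

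**What the plan says.** Section 13.3 (Phase I Study) makes pharmacokinetics the phase I secondary endpoint. It lists half-life, Cmax, AUC, volume and clearance, and states that "volume of distribution, and clearance will be determined using non-compartmental methods". On the analysis set it adds: "These analyses will be performed in all patients accrued to the phase I component of the trial". Section 13.2 expects about 12 phase I patients.

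Section 9.5 sets the sampling:

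- Duvelisib on Day 1: pre-dose, then up to "24 hours following the initial dose of duvelisib on Day 1".
- Both drugs on Day 8: pre-dose, then "0.5, 1, 2, 4, 6, 8, 10, and 24 hours following the initial venetoclax dosing on Day 8".
- On both days: "The 10-hour post dose PK is strongly encouraged, but optional".
- At each later venetoclax escalation in cycle 1: pre-dose, 1 h and 4 h only.

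The drug descriptions supply the kinetics. For venetoclax, Section 8.2.1 reports "Mean harmonic terminal phase half-life from 17 to 41 hours" and a peak at about 5-8 h. For duvelisib, Section 8.1.1 reports "The half-life was 7 hours, regardless of dose" and a peak at about 0.5-2 h. Section 5.1.1 has duvelisib given twice daily, and the drug diary (Appendix F) places the doses in the morning and the evening. No exception for PK days was found, and no rule for which samples enter the terminal slope, how much AUC may be extrapolated, or over which interval AUC is taken.

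**The concern.** By non-compartmental analysis (NCA), half-life comes from a log-linear slope through the last samples. After a single dose, clearance and volume come from that slope and from AUC extrapolated to infinity. All three fail if the samples do not reach far enough into the terminal phase, or if another dose falls among them. Venetoclax raises the first problem and Day 1 duvelisib the second.

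The protocol (Sections 2.5, 5.4.6 and 7.4.1.3) expects a possible CYP3A4 interaction between the two drugs. An unstable venetoclax clearance, or a duvelisib AUC inflated by an uncounted dose, could be misread as an interaction or could hide one.

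**Working it through.** The plan gives no figure for sampling adequacy, so there is none to reproduce.

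**Assumptions not in the documents:** one-compartment oral kinetics; a 12 h duvelisib interval; 15% log-scale residual error in the simulations (5,000 profiles per scenario); 26 h as an intermediate venetoclax half-life; 20% as a customary ceiling on extrapolated AUC.

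**Venetoclax, coverage.** Time from peak to last sample is 24 - 8 = 16 h to 24 - 5 = 19 h. In half-lives this is 16/41 = 0.39 to 19/17 = 1.12. Only the 8 h, 10 h (optional) and 24 h samples lie at or after the end of the Tmax range.

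**Venetoclax, extrapolation.** With ke = ln 2 / half-life, and ka solved from Tmax = ln(ka/ke)/(ka - ke), the fraction of AUC beyond time T is (ka·e^(-ke·T) - ke·e^(-ka·T))/(ka - ke). The simulated half-life is the NCA slope through 8, 10 and 24 h.

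| True half-life | Tmax | AUC beyond 24 h | Estimated half-life, 5th-95th percentile |
|---|---|---|---|
| 17 h | 5 h | 40.5% | 11.5-34.8 h |
| 17 h | 8 h | 43.9% | 13.3-59.1 h |
| 26 h | 5 h | 54.9% | 14.9-104.7 h |
| 26 h | 8 h | 57.1% | 16.3-325.5 h |
| 41 h | 5 h | 68.1% | 18.7 h to not estimable |
| 41 h | 8 h | 69.5% | 19.7 h to not estimable |

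At 41 h, 8-11% of profiles show no positive slope. At 26 h with Tmax 5 h, estimated CL/F runs from 0.32 to 1.42 times the truth. Extrapolation exceeds 20% in at least 99.8% of profiles.

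The result does not depend on slow absorption. With instantaneous absorption the tail is 2^(-24/17) = 38% and 2^(-24/41) = 67%. Staying at or below 20% would need a half-life of at most 24·ln 2/ln 5 = 10.3 h. The later visits do not help, because their last post-dose sample (4 h) precedes the peak.

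**Duvelisib Day 1, with the 24 h sample.** Take the starting level as 1, instantaneous absorption and ke = ln 2/7 = 0.0990 per hour.

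- C(10) = 2^(-10/7) = 0.371.
- C(24) from the morning dose alone = 2^(-24/7) = 0.093. Adding an evening dose at 12 h, 2^(-12/7) = 0.305, gives 0.398, which is 4.3 times the single-dose value and above the 10 h level.
- Fitted half-life: 34 h (points 4, 6, 8, 10, 24), 48 h (6, 8, 24), 59 h (6, 8, 10, 24). Starting at 8 h the line is almost flat (about 207 h).
- Exact single-dose AUC(0-24) = (1 - 0.093)/0.0990 = 9.16. The linear trapezoid with the redosed 24 h value is 6.36 (0-10 h) + 14 × (0.371 + 0.398)/2 = 11.75, a ratio of 1.28. Without the 10 h sample it is 12.34, a ratio of 1.35. Of these excesses, 5 and 8 percentage points are trapezoidal error that a clean profile would also show (9.61 and 9.90 against 9.16).
- If that slope also enters AUC to infinity (points 4-24 h, Tmax 0.5-2 h), CL/F falls to about 0.32 of the truth.

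**Duvelisib without the 24 h sample (Tmax 0.5-2 h).** Without noise, the 4-10 h points return 7.0-7.05 h and the 4-8 h points 7.0-7.1 h. With 15% error and the 10 h sample present, the 5th-95th percentile is about 5-11 h for Tmax 0.5-1 h and 4.5-16 h for Tmax 2 h. Extrapolated AUC is 38-40% from 10 h and 46-49% from 8 h.

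**Duvelisib Day 8.** After a week of twice-daily dosing and with a 7 h half-life, levels are at steady state. CL/F = dose/AUC(0-12), with the pre-dose level standing in for the 12 h value, is within about 1% of the truth without noise and needs no extrapolation.

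**The case against.** The strongest reply is that Section 13.3 commits to none of these errors. It does not say that the 24 h duvelisib sample enters the slope, or that AUC means AUC to infinity. A competent analyst would see the level at 24 h above that at 10 h and recognise redosing. This stands in part: for duvelisib the defect is a missing rule, not a prescribed error. It does not rescue venetoclax. Half-life, clearance and volume are promised there by name, and no choice among the scheduled samples extends coverage much beyond one half-life.

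A reader might infer that these parameters cannot be obtained for either drug and should all be dropped. The documents do not support that. Duvelisib samples to 8-10 h cover more than one 7 h half-life, and Section 9.5 gives a second full profile on Day 8. Even for venetoclax most profiles yield a number; the trouble is its reliability.

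A reader might also infer that the interaction question is lost or the dose finding compromised. Neither follows. Section 13.1 sets the MTD from DLTs. Cmax, venetoclax AUC(0-24), duvelisib AUC(0-12) on Day 8 and pre-dose levels at each escalation all remain available. Venetoclax is never given alone during the PK period, so its half-life has no within-study comparator anyway.

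**Conclusion.** The point holds for venetoclax. With sampling to 24 h, NCA half-life, CL/F and V/F rest on two or three points covering 0.4-1.1 half-lives, and on AUC to infinity that is 41-70% extrapolated. They cannot be reliably estimated.

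For duvelisib it is narrower. The Day 1 24 h sample is not a single-dose sample; treating it as one gives a half-life of roughly 34-59 h (fits starting at 4 or 6 h) instead of 7 h, and an AUC(0-24) about 28% too high (35% without the optional 10 h sample). With that sample excluded, half-life is estimable with moderate precision from Day 1, and apparent clearance from Day 8.

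The venetoclax coverage figure follows from the documents alone. The extrapolated fractions and the duvelisib figures need the one-compartment model, and the duvelisib figures also need an evening dose near 12 h. The simulated spreads also depend on the 15% error. The consequence is confined to a descriptive secondary endpoint in about 12 patients; MTD and CR conclusions are unaffected.

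**What to change.** Amend the phase I paragraph of Section 13.3:

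- **Venetoclax:** by NCA, report only Cmax, Tmax and AUC(0-24). Drop half-life, CL/F and V/F, or estimate them with a compartmental or population model that includes all dose times.
- **Duvelisib, Day 1:** exclude the 24 h sample from the terminal slope and from single-dose AUC. Report Cmax, Tmax and AUC(0-8), with AUC(0-10) where the optional sample exists. Keep half-life from the samples up to 8-10 h and note its limited precision.
- **Duvelisib, Day 8:** take CL/F from steady-state AUC(0-12), using the pre-dose level as the 12 h value. Say that it is measured with venetoclax co-dosed.
- **Both drugs:** call clearance and volume apparent (CL/F, V/F), since dosing is oral, and state the rule for slope points and the limit on extrapolated AUC.

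The cost is wording: no new samples and no change to dosing. The downside is that fewer venetoclax parameters are reported. An analysis rule is also the practical route, because the Synopsis and Section 5 already describe phase I TLS findings in the past tense, so later samples can probably no longer be added.

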***Phase II Study:***

Secondary endpoints in the phase II trial include, response assessments including ORR, defined as partial response and complete response or complete response with incomplete count recovery according to the 2008 IW-CLL or Lugano 2014 criteria the duration of response (DOR) among patients who have achieved a PR or CR/CRi, defined as the time from first response to progression or last follow-up, progression free survival (PFS), defined as the time from treatment start to progression, death or last follow-up, whichever comes first, overall survival (OS), defined as time from treatment start to death or last follow-up, MRD negativity, determined by 4-color flow cytometry with a sensitivity of  $10^{-4}$  and a complete response in the bone marrow at 6 and 12 months, and the association FISH abnormalities, *TP53*, *NOTCH1*, or *SF3B1* mutations, and *IGHV* mutational status with ORR and CR rate.

ORR (defined as proportion of patients who achieve a complete and partial response) will be estimated along with a 95% confidence interval, and rate of best response and MRD will be calculated. For patients who respond to treatment (complete or partial response), duration of response will be calculated from the date of response to the date of progression of disease. Patients still responding at date of last follow-up will be censored. PFS will be calculated as the time from start of treatment to the date of progression, death or last follow-up. OS will be calculated as the time from the start of treatment to the date of death or last follow-up. OS, PFS and DOR will be calculated using Kaplan-Meier methodology. The rate of MRD negativity and pathologic CR/CRi will be estimated along with a 95% confidence interval. The association between baseline characteristics (such as FISH abnormalities, *TP53*, *NOTCH1*, or *SF3B1* mutations, and *IGHV* mutational status) and response will be assessed using Fisher's exact test.

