Participants will be removed from the protocol therapy (treatment) when any of these criteria apply. The reason for removal from protocol therapy, and the date the participant was removed,

CONFIDENTIAL

This document is confidential. Do not disclose or use except as authorized.

must be documented in the case report form (CRF). Alternative care options will be discussed with the participant.

When a participant is removed from protocol therapy, they will remain on study in active follow up for up to one year or until withdrawal of consent, initiation of other CLL or Richter's directed therapy, or death. They will then be followed for survival indefinitely.

When a participant is off of the study completely (no longer in follow up or being followed for survival), the relevant Off-Treatment/Off-Study information will be relayed to the lead site study team, and updated in OnCore.

In the event of unusual or life-threatening complications, treating investigators must immediately notify the Overall PI, *[name]* at [contact], [name].

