### 11.3.3 **Progression free Survival**

**Progression-Free Survival:** Progression-Free Survival (PFS) is defined as the time from registration to the earlier of progression or death due to any cause. Participants alive without disease progression are censored at date of last disease evaluation.

**Overall Survival:** Overall Survival (OS) is defined as the time registration to death due to any cause, or censored at date last known alive.

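### Section 13.3 ends duration of response only at progression, so deaths in response are censored and inflate it; Sections 11.3.3 and 13.3 also define PFS and OS differently

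*Combined protocol and SAP*

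**What the plan says.** Section 13.3 (Phase II Study) describes DOR twice. In the list of secondary endpoints it is "defined as the time from first response to progression or last follow-up". In the analysis paragraph, "duration of response will be calculated from the date of response to the date of progression of disease". The only DOR censoring rule covers patients still in response when last followed. DOR, PFS and OS are all to be estimated by Kaplan-Meier, and no competing-risk method is named.

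The same section gives the other two endpoints with death included: "PFS will be calculated as the time from start of treatment to the date of progression, death or last follow-up" and "OS will be calculated as the time from the start of treatment to the date of death or last follow-up".

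Section 11.3.3 defines PFS and OS again, and differently. PFS "is defined as the time from registration to the earlier of progression or death due to any cause", and "Participants alive without disease progression are censored at date of last disease evaluation". OS "is defined as the time registration to death due to any cause, or censored at date last known alive". Section 11.3.3 does not define DOR.

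Follow-up depends on why treatment stopped. Under Sections 5.5 and 5.6, patients who stop for reasons other than MRD negativity have at most one year of active follow-up, after which "They will then be followed for survival indefinitely". Section 5.6 sets no such limit on disease monitoring for patients who stop with MRD negativity.

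**The concern.** Kaplan-Meier treats a censored patient as someone whose response could have continued. A patient who has died in response cannot continue to respond, so censoring that patient pushes the DOR curve up. Such deaths are plausible here. Section 7.4 reports that in the duvelisib phase I study in relapsed or refractory CLL/SLL, pneumonia and febrile neutropenia were each serious events in 16.4% of patients, and sepsis in 3.6%.

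For PFS and OS, one document holds two time origins. For PFS it also holds two censoring dates, and the term last follow-up in 13.3 is not defined. If it is read as any contact, a survival-only telephone call long after the last disease assessment would count as progression-free time. Two analysts could then report different PFS and OS from the same data, each following the document.

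**Working it through.** The plan states no median, rate or event count for DOR, PFS or OS, so there is no figure of its own to reproduce. The check compares the definitions and then sizes the effects on stated assumptions.

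**1. Definitions side by side**

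| Endpoint | Section 11.3.3 | Section 13.3 |
|---|---|---|
| DOR | not defined | first response to progression; death not named |
| PFS start | registration | start of treatment |
| PFS events | progression or death | progression or death |
| PFS censoring | last disease evaluation | last follow-up (undefined) |
| OS start | registration | start of treatment |
| OS censoring | last known alive | last follow-up (undefined) |

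A responder who dies without recorded progression has no DOR event under either statement in 13.3. With Kaplan-Meier and no rule for death, the literal result is censoring.

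**2. Size of the DOR effect**

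Assumptions (none is in the documents): constant hazards; true median to progression or death of 12 months; f = share of response-ending events that are deaths without progression.

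- Total hazard h = ln 2 / 12 per month. As written, only (1 − f)h is counted.
- Reported median = ln 2 / [(1 − f)h] = 12 / (1 − f).
- Reported 12-month rate = 0.5^(1 − f).

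| f | Reported median (true 12.0 months) | Reported 12-month rate (true 50%) |
|---|---|---|
| 0% | 12.0 | 50% |
| 5% | 12 / 0.95 = 12.6 | 0.5^0.95 = 52% |
| 10% | 12 / 0.90 = 13.3 | 0.5^0.90 = 54% |
| 20% | 12 / 0.80 = 15.0 | 0.5^0.80 = 57% |

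The factor 1/(1 − f) does not depend on the assumed median: at f = 20%, a true 6 months becomes 7.5 and a true 24 months becomes 30.0.

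**3. A small-sample example, without the constant-hazard assumption**

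Take 20 hypothetical responders: progressions at months 3, 6 and 9; deaths in response at months 5, 8 and 11; the other 14 censored at month 18.

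- Deaths censored: 12-month DOR = (19/20) × (17/18) × (15/16) = 84%.
- Deaths as events: 12-month DOR = 14/20 = 70%.

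Censoring these deaths can never lower the curve.

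**4. Start date**

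Each week between registration and first dose adds 7 / 30.44 = 0.23 month to PFS and OS under 11.3.3 compared with 13.3. An assumed gap of 1 to 4 weeks gives 0.2 to 0.9 month (28 / 30.44 = 0.92). Section 10 asks for treatment as soon as possible after registration but states no maximum gap. Section 13.4 excludes participants who never start combination therapy, so everyone analysed has survived this interval.

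**5. PFS censoring date**

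After the first year, scans are about every six cycles or at the investigator's discretion (Section 5, Phase II; Table 9, note 9). Six 28-day cycles are 168 days, or 168 / 30.44 = 5.5 months, so the last scan and the last contact can differ even on treatment. They can differ by more once a patient is in survival-only follow-up. The net effect on PFS has no fixed direction: starting at first treatment shortens it, while censoring at a survival-only contact could raise the late part of the curve. No figure is offered for late PFS.

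**The case against.** **Censoring is an inference.** Section 13.3 never says that deaths in response are censored; it is silent. That is correct. But a patient who dies without progression has no event, and censoring is the only outcome the text leaves. If the plan is instead read as having no rule for death, the text still needs correcting.

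**Progression-only DOR may be deliberate.** Time to progression among responders is a coherent cause-specific quantity, and PFS and OS are reported beside it. However, the plan does not state this intention and names no competing-risk analysis. For CLL/SLL, Section 11.3.1.9 classes death from any cause as treatment failure, which fits poorly with a DOR that ignores it. The overstatement is relative to DOR with death as an event.

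**The PFS and OS conflict is narrow.** The events agree in both sections, and for OS the two censoring dates are nearly equivalent. This stands: the OS conflict is the start date only, and the PFS conflict is the start date plus the censoring date.

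**The start-date gap is bounded.** Section 3.1 requires eligibility laboratory tests within 28 days before therapy starts, which implies a gap of about four weeks at most unless tests are repeated. That matches the upper end of the range used here. It limits the size but does not remove the discrepancy.

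**The consequences are modest.** These are descriptive secondary endpoints in a non-randomised trial, with assumed inputs for every magnitude. This also stands.

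**Conclusion.** The concern holds. As written, Section 13.3 yields a DOR that is biased upwards whenever a responder dies without recorded progression. The direction is certain and the size is not. Under constant hazards the median is inflated by 1/(1 − f): about 5% at f = 5%, 11% at f = 10% and 25% at f = 20%, with no bias at f = 0. The values of f are assumptions.

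Sections 11.3.3 and 13.3 give different start dates for PFS and OS, worth 0.2 to 0.9 month for an assumed gap of 1 to 4 weeks. They also give different censoring dates for PFS, with an effect that is not quantified and whose net direction is not fixed.

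The two-stage CLL/SLL rule and the single-stage Richter's rule depend on complete response and are unaffected.

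**What to change.** In Section 13.3, define DOR as the time from first documented response to the earlier of progression or death from any cause. If a progression-only duration is intended, say so and name a competing-risk analysis with death in response as the competing event.

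In both 11.3.3 and 13.3, use one start date for PFS and OS, for example the start of study treatment. Censor PFS and DOR at the last adequate disease evaluation, say what counts as adequate, and censor only OS at the date last known alive. Replace last follow-up accordingly. The same edit should state how PFS and DOR handle patients who begin other CLL or Richter's therapy or leave for transplant, since Sections 5 and 5.5 foresee both.

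The cost is wording in two sections. The dates needed are already collected, and sample size and the complete-response decision rules do not change. Reported DOR, and possibly late PFS, may become slightly less favourable.
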